### 8.2. Setting

The data used for the analyses includes all patients aged  $\geq 18$  years with at least one filled prescription of an oral targeted therapy relevant for treating mRCC registered in the Swedish Prescribed Drug Register between 01 July 2005 (there is no data available in the register before this date) and 31 December 2019. The Anatomical Therapeutic Chemical (ATC) codes for the oral drugs relevant for treating mRCC are the following: L01XE04 (sunitinib), L01XE05 (sorafenib), L01XE11 (pazopanib), L01XE17 (axitinib), L01XE10 (everolimus), L01XE26 (cabozantinib), L01XE34 (tivozanib), L01XE29 (lenvatinib).

Selecting patients based on dispensed prescriptions ensure that all patients that have prescriptions on the relevant drugs are included in the analyses. The first identified prescription date will correspond to the patient's index date that is relevant for capturing the age.

The PDR does not provide any information on mRCC, which is the area of interest in this study. The analysis therefore combines the PDR, the SCR and the NPR with the aim to identify the mRCC cohort. The patients identified in the PDR that also are identified in the SCR with the International Classification of Diseases and Related Health Problems

PFIZER CONFIDENTIAL

(ICD)-7 diagnosis codes I800 or I809 and ICD-10 codes C64.0 and C64.9 from 01 January 2000 until 31 December 2019; excluding ICD-7 code I801 (cancer of the renal pelvis) will be included in the analysis set.

The mRCC cohort derived above will then be further restricted into two different analysis sets that will be used to carry out the analyses.

[figure not shown]
- Analysis Set 1: patients treated with sunitinib in the first line mRCC setting
- Analysis Set 2: patients treated with axitinib in the second line mRCC setting

Analysis Set 1 will be derived in the following way, from the full mRCC cohort described above, individuals will be selected that have sunitinib as the first filled prescription (the earliest date) of the relevant drugs: (sunitinib), L01XE05 (sorafenib), L01XE11 (pazopanib), L01XE17 (axitinib), L01XE10 (everolimus), L01XE26 (cabozantinib), L01XE34 (tivozanib), L01XE29 (lenvatinib), and L03AB (cytokines medication). L03AB used to be a common treatment for this patient group in the beginning of the investigated period and is therefore needed to identify the correct treatment line.

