**Table 1. Overview of study variables**

Variable	Role	Data source(s)	Operational definition
Total number of sunitinib 1L patients	Outcome	Prescription Register	Number of sunitinib users with at least one filled prescription (in total and per year over time)
Number of sunitinib 1L 4:2 schedule users	Outcome	Prescription Register	Number of sunitinib users that started on a 4:2 schedule and never had a modification in the schedule (total and per year over time)
Number of sunitinib 1L 2:1 schedule users	Outcome	Prescription Register	Number of sunitinib users that started on a 2:1 schedule and never had a modification in the schedule (total and per year over time)
Number of sunitinib 1L patients that was switched from a 4:2 schedule to a 2:1 schedule	Outcome	Prescription Register	Number of sunitinib users that started on a 4:2 schedule and later was switched to a 2:1 schedule, in total and per year over time

PFIZER CONFIDENTIAL

Total number of axitinib second line patients	Outcome	Prescription Register	Number of axitinib 2L users with at least one filled prescription (in total and per year over time)
Gender	Baseline characteristics	Prescription Register	Male/Female (binary)
Age	Baseline characteristics	Prescription Register	Age will be defined as age at the date of first filled prescription of relevant mRCC medication (continuous; years).
Year of treatment initiation	Baseline characteristics	Prescription Register	Defines the year the treatment was initiated.
Region	Baseline characteristics	Prescription Register	County council of the prescribing physician at first prescription date (categorical), see Table 6 in Annex 3
Time to treatment discontinuation	Outcome	Prescription Register	Time from date of first filled prescription to the end of the prescribed supply, or prescription of other ATC code or death if either of these happen before (details in Section 8.2).
Overall survival	Outcome	Cause of Death Register, Prescription Register	Time from date of first filled prescription of the relevant drug to date of death (number of days) where death is defined as all-cause death; If no date of death is recorded, data is censored at latest available date in data.

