**Table 3. Variables extracted from the NBHW**

Variable	Explanation	Data source(s)
ICD7	ICD-7 code	Swedish Cancer Register
ICD9	ICD-9 code	Swedish Cancer Register
ICDO10	ICD-O/2-10	Swedish Cancer Register
ICDO3	ICD-O/3	Swedish Cancer Register
ALDER	Age at diagnosis	Swedish Cancer Register
M	Spread of tumor at diagnosis, distant metastases	Swedish Cancer Register
N	Spread of tumor at diagnosis, Lymph nodes	Swedish Cancer Register
DIADAT	Date of RCC diagnosis	Swedish Cancer Register
DODSDAT	Date of death	Swedish Cancer Register
DODSDATN	Date of death numeric	Swedish Cancer Register
KON	Gender	Swedish Cancer Register
SJUKHUS	Hospital where diagnosis was set	Swedish Cancer Register
DODSDAT	Date of death	Swedish Cause of Death Register
ALDER	Age at visit	National Patient Register
AR	Year of visit	National Patient Register
MVO	Medical focus area	National Patient Register
SJUKHUS	Hospital	National Patient Register
DIAGNOS	Diagnosis	National Patient Register
HDIA	Main diagnosis	National Patient Register
KON	Sex	National Patient Register

PFIZER CONFIDENTIAL

INDATUMA	Date for start of visit	National Patient Register
OP	Surgery	National Patient Register
UTDATUMA	Date for end of visit	National Patient Register
VTID	Duration of care	National Patient Register
ALDER	Age at the end of the year	Swedish Prescribed Drug Register
ARBLAN	The region of the prescribing clinic	Swedish Prescribed Drug Register
FDATE	Prescription date	Swedish Prescribed Drug Register
EDATE	Dispense date	Swedish Prescribed Drug Register
ANTAL	Number of packages	Swedish Prescribed Drug Register
DOSER	Dosing instructions	Swedish Prescribed Drug Register
EXPLAN	Region/County of dispensing pharmacy	Swedish Prescribed Drug Register
FVARUNR	Dispensed drug goods number	Swedish Prescribed Drug Register
ATC	ATC code	Swedish Prescribed Drug Register
PRODUKT	Name of product	Swedish Prescribed Drug Register
FORPS	Package size	Swedish Prescribed Drug Register
STYRKALF	Strength of the product	Swedish Prescribed Drug Register
STYRKAENHET	Unit of the strength	Swedish Prescribed Drug Register
KON	Gender	Swedish Prescribed Drug Register

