### **8.7. Data analysis**

An overview of the planned analyses are presented in this section. In general, the study is descriptive and does not involve hypothesis testing. Any major modifications of primary endpoint definitions or their analyses would be reflected in a protocol amendment.

Time-to-event analyses will be carried out using standard Kaplan-Meier methods. Kaplan-Meier survival functions will be estimated with relevant events as failure. Time-to-event tables

PFIZER CONFIDENTIAL

and Kaplan-Meier curves will be presented. Log-Rank tests will be used to assess differences across cohorts. In addition, to explore potential determinants of persistence /drug survival and to adjust for differences across cohorts, semi-parametric cox-proportional hazard models will be deployed based on different covariates.

Relevant events for this study include:

- Time to treatment discontinuation
- Death

Time-to-event tables will present:

- Failed/Censored n (%).
- Median time to event.
- 95% confidence intervals of median.
- The 25th and 75th percentiles (q1 and q3).
- Min and max.
- n at risk by unit.
- Time point estimates and 95% Confidence Intervals (CI)by unit.

[figure not shown]
As described in Section 8.2 the analyses will be carried out based on two analysis sets.

Analysis Set 1 consists of all patients indentified with sunitinib as the first line treatment.

Analysis Set 2 consists of all patients indentified with axitinib as the second line treatment.

The Table 4 below displays the output from the time to treatment discontinuation and overall survival analyses that will be carried out based on Analysis Set 1. The output will be presented for three different dosing schemes of interest, patients that started on a 4:2 schedule and that did not switch, patients that started on a 4:2 schedule but later switched to a 2:1 schedule and patients that started on a 2:1 schedule and did not switch. Output will also be presented as Kaplan Meier (KM) curves.

PFIZER CONFIDENTIAL

[figure not shown]

To explore potential determinants drug survival and to adjust for differences across cohorts, semi-parametric cox-proportional hazard models will be deployed based on the following covariates: age, gender, year of treatment initiation, region.

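### Analysis Set 1: the Cox models meant to adjust between sunitinib schedules contain no disease variable, although M, N and date of diagnosis are extracted

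*Combined protocol and SAP*

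**What the plan says.** Section 8.7 calls the study descriptive and free of hypothesis testing, but then plans comparisons: "Log-Rank tests will be used to assess differences across cohorts". Cox models are added "to explore potential determinants of persistence /drug survival and to adjust for differences across cohorts". For Analysis Set 1 the section then closes the list: "semi-parametric cox-proportional hazard models will be deployed based on the following covariates: age, gender, year of treatment initiation, region".

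Table 1 labels the same four variables, and no others, as baseline characteristics. Table 4 reports three groups: started on 4:2 without switching, started on 4:2 and switched to 2:1, and started on 2:1. Section 8.2.1 takes the schedule from the prescriber's dosing instruction.

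Table 3 lists three fields from the Swedish Cancer Register that describe the disease: M ("Spread of tumor at diagnosis, distant metastases"), N ("Spread of tumor at diagnosis, Lymph nodes") and DIADAT ("Date of RCC diagnosis").

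**The concern.** Schedule is not randomised. Section 6 says the study will look at how drug survival and overall survival depend on the dosing schedule, and it reports earlier evidence of better tolerability on 2:1, which is a plausible reason for selective prescribing. Age, gender, calendar year and county cannot stand in for extent of disease in a metastatic cancer cohort.

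If the schedule groups differ in, say, the share with metastases at diagnosis, the adjusted schedule hazard ratio absorbs that difference, and no planned table would reveal it. Section 8.9 names selection and misclassification bias. It mentions missing progression data only in connection with treatment line, and it does not name confounding by disease status. A reader would see an adjusted result with no sign that disease was left out, although relevant fields were in the extract.

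The point concerns Analysis Set 1 only. Table 5 has a single axitinib column, so there is no between-group contrast to confound there.

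**Working it through.** **1. Cross-reading the tables.** The plan gives no figure to reproduce; the question is what the model contains.

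| Variable | Extracted (Table 3) | Baseline characteristic (Table 1) | Cox covariate (8.7) | In Table 4 |
|---|---|---|---|---|
| Age, gender, region | yes | yes | yes | no |
| Year of initiation | from dispensing date | yes | yes | no |
| M at diagnosis | yes | no | no | no |
| N at diagnosis | yes | no | no | no |
| Date of diagnosis | yes | no | no | no |

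The diagnosis date may serve the cohort window in Section 8.2 (codes "C64.0 and C64.9 from 01 January 2000 until 31 December 2019"), but it is neither modelled nor tabulated. M and N have no stated role at all.

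**2. How large could the bias be?** Take a true schedule hazard ratio of 1.00 and one omitted binary factor with hazard ratio h, prevalence p1 in one group and p0 in the other. Approximately, the apparent hazard ratio is [1 + p1(h - 1)] / [1 + p0(h - 1)]. The values of h, p1 and p0 are assumptions; none is in the documents. A simulation alongside used an assumed 700 versus 200 patients, exponential times, administrative censoring, a Cox model with schedule only, and 1,000 replicates per cell.

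| h | p1 vs p0 | Formula | Simulated, about 60% events | Simulated, about 90% events |
|---|---|---|---|---|
| 2.0 | 0.3 vs 0.5 | 1.30/1.50 = 0.867 | 0.869 | 0.882 |
| 2.0 | 0.4 vs 0.5 | 1.40/1.50 = 0.933 | 0.938 | 0.940 |
| 1.5 | 0.3 vs 0.5 | 1.15/1.25 = 0.920 | 0.922 | 0.931 |
| 1.5 | 0.4 vs 0.5 | 1.20/1.25 = 0.960 | 0.965 | 0.963 |
| 2.0 | 0.5 vs 0.3 | 1.50/1.30 = 1.154 | 1.142 | 1.139 |
| 2.0 | 0.5 vs 0.4 | 1.50/1.40 = 1.071 | 1.069 | 1.063 |
| 1.5 | 0.5 vs 0.3 | 1.25/1.15 = 1.087 | 1.091 | 1.081 |
| 1.5 | 0.5 vs 0.4 | 1.25/1.20 = 1.042 | 1.032 | 1.041 |

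The standard error of the log hazard ratio was 0.104-0.107 at about 60% events and 0.085-0.086 at about 90%. Bias relative to standard error therefore runs from ln(1.032)/0.104 = 0.30 to ln(1.139)/0.085 = 1.53.

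**3. Can the sample carry more covariates?** Section 8.5 expects about 1,000 first-line sunitinib patients. Table 6 has 21 counties (20 parameters). Year as categories over 2005-2019 takes 14; Table 1 does not say how year is coded, so this is the costlier reading.

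- Current list plus schedule: age 1 + gender 1 + year 14 + region 20 + schedule 2 = 38.
- Adding M (2, with an unknown level), N (2) and a linear time term (1): 43. With three time categories (2): 44.
- With an assumed 60-90% having events (600-900): 600/38 = 15.8 to 900/38 = 23.7 events per parameter now, and 600/44 = 13.6 to 900/44 = 20.5 after the change.

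**4. Range of time since diagnosis.** Diagnoses count from 1 January 2000. A patient starting on 1 July 2005 can have at most 5.5 years since a counted diagnosis; one starting on 31 December 2019 can have 20.0. The possible range thus depends on year of initiation, which matters for how the variable is coded.

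**The case against.** The strongest reply is that the contrast at issue is never written down. Schedule is not in the covariate list, and the Cox sentences name only persistence or drug survival, not overall survival. The adjustment wording is repeated for Analysis Set 2, where there is nothing to adjust between, so it may be boilerplate. This stands as a qualification: the schedule term and an adjusted survival model are both inferred. It does not remove the point, because a model of determinants of drug survival in this population would still hold no disease variable.

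Second, nothing in the documents ties M, N or time since diagnosis to schedule choice. Tolerability points to frailty, for which age is arguably the closer proxy. That is fair, and it is why the size and direction of bias are left open.

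Third, the illustration uses the standard error of a schedule-only model. If the other covariates explained an assumed 30% of the variance of schedule, the standard error would rise by a factor of 1/sqrt(0.7) = 1.20 and the upper ratio would fall from 1.53 to about 1.28. Adjustment for year could also absorb part of a calendar-driven imbalance. Both points stand.

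Fourth, the remedy is imperfect. M and N describe spread at diagnosis, not at sunitinib start. Section 8.8 gives completeness for the register, not for these fields, and an unknown category can leave confounding behind. Section 8.2.1 excludes other sunitinib schedules from the analysis, so events per parameter will be somewhat below the figures above. Hazard ratios are non-collapsible, so a shift between the two models is not purely confounding.

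Finally, the study is labelled explorative and descriptive, and Section 8.7 calls itself an overview. That lowers the stakes, but a model given an adjustment purpose needs a covariate list that can serve it.

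**Conclusion.** The concern holds. The covariate list for Analysis Set 1 is closed and contains no disease variable, Table 1 defines none as a baseline characteristic, and three relevant fields in the extract go unused. The size and direction of any bias cannot be derived from the documents. Under the assumptions shown, a null schedule effect would appear as 0.87-0.96, or 1.04-1.15 with the imbalance reversed, by formula. By simulation the ranges are 0.87-0.97 and 1.03-1.14. This is modest, but at the upper end it is large enough to change how a contrast is read. The practical weight rests on the inference that schedule enters the Cox model. The change should be made before analysis. It will reduce confounding, not remove it.

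**What to change.** For Analysis Set 1 only.

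**Section 8.7**
- Name schedule group as a term in the Cox model for time to discontinuation and, if an adjusted survival model is intended, in that model too.
- Add M (M1, M0, unknown), N (with an unknown category) and time from DIADAT to first fill. Enter time in categories or a flexible form. Cut-points below 5.5 years, for example 1 and 3 years, keep every category reachable in every initiation year.
- State how a DIADAT later than the first fill is handled, since Section 8.2 does not require diagnosis to come first.
- Report the four-covariate model alongside, noting that differences between the two are not purely confounding.

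**Table 1 and output.** Define these variables as baseline characteristics and tabulate them by schedule group, with the share unknown.

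**Section 8.9.** State that M and N are measured at diagnosis, do not measure disease burden at sunitinib start and may be incomplete; that the top category of time since diagnosis spans different lengths by initiation year; that residual confounding remains; and that baseline adjustment does not repair defining switchers by an event after treatment start.

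**Cost.** Low: the fields are already listed in Table 3 and the edits are a few lines. The model grows from about 38 to 44 parameters. The downsides are some missing M and N values and a small loss of precision that has not been quantified for the planned model.

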**Table 4. Time to treatment discontinuation and OS, first line treatment with sunitinib**

	L01XE04 Started on 4:2 schedule, no switch N=xxx	L01XE04 Started on 4:2 schedule, switch to 2:1 schedule N=xxx	L01XE04 Started on 2:1 schedule N=xxx
Censored n (%)	xx (xx.x)	xx (xx.x)	xx (xx.x)
Failed n (%)	xx (xx.x)	xx (xx.x)	xx (xx.x)
Survival time (Unit)			
Median (KM)	xx.x	xx.x	xx.x
95% CI of median (KM)	xxx.x ,xxx.x	xxx.x ,xxx.x	xxx.x ,xxx.x
Q1, Q3 (KM)	xxx.x ,xxx.x.	xxx.x ,xxx.x.	xxx.x ,xxx.x
Min , Max	xx.x ,xx.x	xx.x ,xx.x	xx.x ,xx.x
Kaplan-Meier survival point estimates – n at risk, % (95% CI)			
1 unit	x, x.xx (x.xx,x.xx)	x, x.xx (x.xx,x.xx)	x, x.xx (x.xx,x.xx)
2 unit	x, x.xx (x.xx,x.xx)	x, x.xx (x.xx,x.xx)	x, x.xx (x.xx,x.xx)
.	.	.	.
.	.	.	.
.	.	.	.
n units	x, x.xx (x.xx,x.xx)	x, x.xx (x.xx,x.xx)	x, x.xx (x.xx,x.xx)

PFIZER CONFIDENTIAL

[figure not shown]
The Table 5 below displays the output from the time to treatment discontinuation and overall survival analyses that will be carried out based on Analysis Set 2. Output will also be presented as KM curves.

To explore potential determinants drug survival and to adjust for differences across cohorts, semi-parametric cox-proportional hazard models will be deployed based on the following covariates: age, gender, year of treatment initiation, region.

**Table 5. Time to treatment discontinuation and OS, second line treatment with axitinib**

	L01XE All 2L patients N=xxx
Censored n (%)	xx (xx.x)
Failed n (%)	xx (xx.x)
Survival time (Unit)	
Median (KM)	xx.x
95% CI of median (KM)	xxx.x , xxx.x
Q1, Q3 (KM)	xxx.x , xxx.x
Min, Max	xx.x , xx.x
Kaplan-Meier survival point estimates – n at risk, % (95% CI)	
1 unit	x, x.xx (x.xx,x.xx)
2 unit	x, x.xx (x.xx,x.xx)
.	.
.	.
.	.
n units	x, x.xx (x.xx,x.xx)

PFIZER CONFIDENTIAL

## **8.8. Quality control**

Data to be used in this study will be extracted from the registers managed by the NBHW and will be of the highest quality. The SCR has nearly 100% completeness and the coverage for inpatient data is almost 100% and nearly 80% for outpatient data.

Data will be ordered through a so-called research request, assessed by the NBHW after ethical approval of the study protocol. Data will be released on an individual basis but with a serial number instead of a social security number, thus preventing individual patients from being identified. Data will be treated with privacy and according to the Swedish Personal Data Act. It is the responsibility of the NBHW to ensure completion of, and to review and approve all the data, and to verify that data is verified to source data.

[figure not shown]
Quality control of data extraction will be done by reviewing of critical variables. Variables will be checked against the delivery specification from the NBHW. Errors will be listed, rectified, and sent to NBHW for correction. Further, the errors will be rectified in the analysis database. Pfizer will perform all programming of the final analysis data set, study database. Data management at Pfizer is tracked so that data editing, i.e. correction, and other data corrections in the preparation of the analysis data sets will be summarized.

The original data extraction from NBHW, or any copy, are the sole property of Pfizer and should not be made available, without written permission from Pfizer, in any form to third parties except for authorized representatives of Pfizer or appropriate authorities.

## **8.9. Limitations of the research methods**

The retrospective design entails a risk of bias in the analyses, especially selection and misclassification bias. Furthermore, information on medication not dispensed on prescription (medication administered in a hospital) is not available at the NBHW. This will have as a consequence that potentially not all patients treated with oral targeted mRCC drugs are included in the analysis. Selecting patients based on dispensed prescriptions and a registered RCC diagnosis might have the consequence that some included patients also suffer from other malignancies for which they were treated with one of the specified drugs. However, we

PFIZER CONFIDENTIAL

believe that risk to be small. Insights from previous studies using this type of data (Wahlgren et al (2013) and Lindskog et al (2017)) will help us handle this in the best way possible. One additional limitation that concerns the definition of treatment line is that the data only allows us to evaluate the chronological order of received treatments, but no data on disease progression is available.

## **8.10. Other aspects**

Not applicable.

# **9. PROTECTION OF HUMAN SUBJECTS**

## **9.1. Patient information**

Data will be presented on an aggregate level and will not be possible to track individual patients.

The variable DOSER will go through manual review, data is unstructured data that require human review.

All parties will comply with all applicable laws, including laws regarding the implementation of organizational and technical measures to ensure protection of patient personal data. Such measures will include omitting patient names or other directly identifiable data in any reports, publications, or other disclosures, except where required by applicable laws.

To protect the rights and freedoms of natural persons with regard to the processing of personal data, when study data are compiled for transfer to Pfizer and other authorized parties, any patient names will be removed and will be replaced by a single, specific, numerical code. All other identifiable data transferred to Pfizer or other authorized parties will be identified by this single, patient-specific code. In case of data transfer, Pfizer will maintain high standards of confidentiality and protection of patients' personal data consistent with the vendor contract and applicable privacy laws.

PFIZER CONFIDENTIAL

